### 1.2. Secondary Objectives

1.2.1. To examine the impact of an eHealth intervention for insomnia on the clinical severity of insomnia symptoms in adult survivors of childhood cancer.

Hypothesis 1.2.1.: A larger proportion of survivors randomized to the CBTi intervention will no longer meet clinical criteria for insomnia post-intervention compared to survivors randomized to online patient education.

1.2.2. To determine whether treatment of insomnia symptoms will improve neurocognitive function in adult survivors of childhood cancer with both insomnia and neurocognitive impairment.

Hypothesis 1.2.2.a.: Survivors randomized to an eHealth CBTi intervention will report significantly fewer symptoms of neurocognitive impairment post-intervention compared to survivors randomized to online patient education only.

Hypothesis 1.2.2.b.: Improvement in insomnia symptoms will mediate the association between intervention status (CBTi vs. online patient education) and improved neurocognitive function post-intervention.

Hypothesis 1.2.2.c.: Symptoms of emotional distress and cardiac health will be associated with improved insomnia symptoms and neurocognitive function.

1.2.3. To explore the mediating effects of improved neurocognitive function, emotional distress, and cardiovascular health on the association between insomnia symptoms and quality of life.

Hypothesis 1.2.3.a.: Survivors with improved insomnia symptoms following completion of an eHealth CBTi intervention will report better health-related quality of life compared to survivors without improved insomnia symptoms.

Hypothesis 1.2.3.b.: Neurocognitive function, symptoms of emotional distress, and biomarkers of cardiovascular health following completion of the eHealth CBTi intervention will mediate the association between improved insomnia symptoms and quality of life 6-months post-intervention.

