#### **3.1. Inclusion Criteria**

##### **3.1.1. Enrollment in CCSS**

##### **3.1.2. Between the ages of 18 and 65 years old**

##### **3.1.3. Meeting at least one of the following three insomnia criteria:**

###### **3.1.3.1 Clinically significant insomnia (i.e. score $\geq 8$ on the Insomnia Severity Index)**

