###### **3.1.3.2 Delayed sleep onset latency (SOL) (i.e. cannot get to sleep within 30 minutes, three or more times a week)**

###### **3.1.3.3 Excessive wake after sleep onset (WASO) (i.e. nighttime awakenings lasting a total of at least 30 minutes, three or more times per week)**

##### **3.1.4. Neurocognitive impairment (i.e. score $\geq 84^{\text{th}}$ %ile of sibling normative data in at least one domain on the CCSS-NCQ)**

- 3.1.5. Regular access to the internet (at least 2-3 days per week)
- 3.1.6. Access to a desktop computer or a laptop
- 3.1.7. Access to a smart phone (android or iPhone), tablet or iPad with Bluetooth Low Energy BLE 4.2 or higher.
- 3.1.8. Ability to read and speak English

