### **3.5. Procedures for Identifying and Randomizing Research Participants**

Prior to initiating the study, team members will be trained on the protocol and study procedures. The background to the study, study procedures, consent processes for the online or the verbal consent, data transfer, and plans to monitor intervention integrity and data quality will be part of the training.

[figure not shown]
Following the study preparation, initial screening for eligibility, consent and additional eligibility verification for the research participants will begin. Once consented and eligibility is confirmed, participants will be randomized using a permuted-block method with random block sizes, stratified on sex, age (<40 vs.  $\geq 40$ ), and cranial radiation therapy (Y/N). Following randomization, participants will complete the remote cognitive assessment, will provide a blood sample using the Dried Blood Spot (DBS) method and wear a WHOOP wrist monitor for 7 to 11 consecutive days. Following the remote evaluation, they will receive a direct link to access the SHUTi program or online patient education (per randomization).

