### 9.1. Summary of Primary and Secondary Objectives

#### Statistical Analysis

A randomized controlled design will be employed for the proposed study. We plan to enroll a total of 352 survivors (176 of each sex), and assuming 10% drop out by the post-intervention 9-week assessment, we will have a total of 320 survivors (160 of each sex) remaining for evaluation. Balance of patient characteristics between study arms will be evaluated and if necessary, adjusted comparisons will be carried out.

The primary endpoint of the study will be the ISI measure of insomnia severity represented as described above. The difference in score from baseline to post-intervention (10 weeks) and baseline to 6 months post-intervention will be calculated and the mean of these differences compared between study arms using linear regression (adjusted for stratification factors). The primary time point of interest will be at 10 weeks, with a secondary endpoint evaluating maintenance at 6 months after intervention. Due to potential sex differences in insomnia and cognition, *a priori* we plan to carry out all analyses and report results separately by sex. Our study is not powered to detect meaningful interaction effects, but if we deem that the effects are reasonably comparable between sexes we will consider presenting combined analysis to increase precision of the estimate. Because this is a randomized trial we expect analyses to be simple and directed towards ascertaining controlled and generalizable intervention effects. The primary endpoint will be considered significant at the two-sided 0.05 level. Estimates of intervention effects (mean differences) will be presented along with associated confidence intervals and two-sided p-values.

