Because mean scores do not reflect the number of survivors who have clinically significant insomnia symptoms, secondary analyses of sleep will compare the proportion of survivors who no longer meet the clinical criteria for insomnia (ISI  $\leq 7$ ) between study arms post-intervention (10 weeks) and at 6 months (noting that 100% of eligible participants will meet the criteria at randomization), using logistic regression models. Additional measures of sleep will also be summarized and compared (sleep diary, actigraphy, fatigue, daytime sleepiness) from baseline, post-intervention, and 6 months. Using the same analytic framework as above, we will evaluate the effect of study intervention on the secondary endpoints of neurocognitive impairment: patient reported (Task Efficiency, Memory, Emotional Regulation) and directly assessed (attention, memory, and executive function) with continuous outcome measures. Additional analyses relevant to secondary objectives focus on better understanding the associations and mediating relationships between the CBTi intervention, insomnia, neurocognition, emotional distress, cardiovascular risk indices and HRQoL (see Figure 2 for theoretical framework).

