direct relationships between change in ISI (baseline to post-intervention) with emotional distress and cardiac health indices at postintervention time points and with HRQoL measures. To establish whether a mediation relationship exists, we will follow standard methodology by 1) establishing that there is an association between the causal variable (e.g. CBTi intervention) and the outcome (e.g. neurocognitive impairment), 2) establishing the association between the causal variable and the mediator and 3) showing that the mediator is associated with the outcome variable in a model with the causal variable included and 4) in the same model as used to evaluate step 3, determine that the relationship between the causal variable and the outcome variable is attenuated by inclusion of the mediator in the model. We do not expect to observe complete mediation in any of our investigations. Specifically, the above methodology will be used to test hypothesis 1.2.2.b with the causal variable defined as CBTi intervention, mediator as change in insomnia (ISI) and outcomes as neurocognitive indices. Hypothesis 1.2.2.c will consider change in insomnia as the causal variable, neurocognitive function indices, emotional distress symptoms and cardiovascular risk indices as mediators for the outcome HRQoL at 6 months. In addition to the stepwise model-based approach outlined above, we will also evaluate relationships using Structural Equation Modelling (SEM) approaches to evaluating mediation, which would allow simultaneous evaluation of the multiple pathways and classes of variables together in a single model, with improved power, allowing estimates of direct and indirect effects calculated from each. All effects size estimates (mean differences and/or odds ratios) will be presented along with associated confidence intervals and two-sided p-values, both unadjusted and adjusted for multiple comparisons. Primary therapies for childhood cancer have been associated with insomnia and study outcomes (neurocognitive morbidities, emotional distress, cardiovascular risk). Because our study inclusion criteria require that survivors have observed neurocognitive deficits we do not expect differential responses to SHUTi by previous childhood cancer treatment exposures. However, chemotherapy exposures and radiation doses are abstracted from medical records and cumulative doses of methotrexate (high dose and intrathecal), cytarabine, and cranial radiation will be included as covariates in relevant analyses. In addition, we will conduct sensitivity analyses to examine their contributions to treatment response.

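### The ISI ≤7 remission analysis assumes everyone starts with insomnia on the ISI, but the entry rule admits people already at ISI ≤7 and no rule says how to count them

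*Combined protocol and SAP*

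**What the plan says.** Hypothesis 1.2.1 (Section 1.2) predicts that more survivors in the CBTi arm "will no longer meet clinical criteria for insomnia post-intervention" than in the education arm. Section 9.1, Statistical Analysis, makes this operational as ISI ≤7, compared between arms by logistic regression at 10 weeks and at 6 months, "noting that 100% of eligible participants will meet the criteria at randomization".

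Section 3.1.3 sets the insomnia entry rule as "Meeting at least one of the following three insomnia criteria". The three are ISI ≥8; taking more than 30 minutes to fall asleep at least three times a week; and excessive wake after sleep onset, described as "nighttime awakenings lasting a total of at least 30 minutes, three or more times per week". The exclusions in Section 3.2 contain no ISI threshold.

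Two statements in Section 9.1 bear on adjustment. The first is general: "Balance of patient characteristics between study arms will be evaluated and if necessary, adjusted comparisons will be carried out". The second says that cumulative methotrexate, cytarabine and cranial radiation doses "will be included as covariates in relevant analyses". The randomization strata in Section 3.5 are sex, age and cranial radiation.

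**The concern.** The entry rule and the outcome use different definitions of insomnia. Entry is satisfied by any one of three criteria, while follow-up is scored on the ISI alone. Someone who enters through the sleep-onset or night-waking route with an ISI of 0 to 7 already satisfies the remission definition at randomization.

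The 100% remark is there to establish that everyone begins as a non-remitter. Since the entry rule does not ensure that, the denominator of the Hypothesis 1.2.1 analysis is undefined for these people. Two analysts could build different denominators from the same data, and the choice could be made after results are seen. If low-ISI entrants are counted as remitted whenever they score ≤7 at follow-up, both arms' remission rates generally rise and the contrast between arms generally falls.

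**Working it through.** **Step 1: does 100% follow from the entry rule?** Entry requires (ISI ≥8) or (delayed onset) or (excessive waking). That disjunction does not imply ISI ≥8, so 100% does not follow on the outcome's scale. Reading the criteria as the three-part entry rule makes 100% true by definition, but follow-up is then scored on something else, and the mismatch has only moved.

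**Step 2: does any other text supply the rule?** Of the adjustment statements, one is conditional and the other names treatment doses. Neither names baseline ISI, and a covariate would not settle the denominator. Baseline ISI is not a stratum. Read literally, no longer meeting the criteria would exclude people who never met them on the ISI, but no section says so.

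**Step 3: inputs for the size.** From the documents (Section 9.1, Power and sample size): 80 per arm per sex at 10 weeks, about 70 at 6 months, and 160 per arm pooled. The plan's continuous-endpoint figures reproduce from these: for 0.45 SD at 80 per arm I get 81.2% power, for 0.48 at 70 per arm 81.0%, and for 0.31 at 160 per arm 79.2%. The plan gives no power figure for the remission endpoint. Not in the documents, hence assumed:

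- q, the share entering at ISI ≤7: 2% to 20%
- remission among those entering at ≥8: t = 45% (SHUTi), c = 22% (education)
- share of low-ISI entrants still at ≤7 at follow-up: s = 95% in both arms

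**Step 4: formulas when everyone is counted.**

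- P_T = (1−q)t + q·s_T and P_C = (1−q)c + q·s_C
- Risk difference = (1−q)(t−c) + q(s_T−s_C), which is (1−q)(t−c) when the staying rates are equal

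Power is from the two-proportion arcsine formula, two-sided 0.05. The restricted analysis uses t and c with (1−q)N per arm.

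At q = 10%: P_T = 0.9×0.45 + 0.1×0.95 = 0.500; P_C = 0.9×0.22 + 0.1×0.95 = 0.293; difference 0.207 instead of 0.230; odds ratio 2.41 instead of 2.90.

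| q | 80/arm: all vs restricted | 70/arm: all vs restricted |
|---|---|---|
| 0 | 88% | 83% |
| 2% | 86% vs 87% | 81% vs 83% |
| 5% | 83% vs 86% | 77% vs 81% |
| 10% | 77% vs 84% | 71% vs 79% |
| 20% | 65% vs 80% | 59% vs 74% |

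Pooled at 160 per arm: 98% vs 99% at q = 5%, and 97% vs 99% at q = 10%. At q = 20% and 80 per arm the odds ratio is 2.12.

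**Step 5: sensitivity to the staying rates.** At q = 10% and 80 per arm, with 95% (SHUTi) vs 85% (education) staying, power is 81% vs 84%. With 95% vs 75% it is 85% vs 84%, so there is no loss.

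**Step 6: the only remission contrast in the documents.** Section 2.2 cites a 44-person wait-list trial in which 73% of SHUTi users and no controls reached the no-insomnia category; the cut-off is not stated there. With s = 95%, q = 10% gives 75.2% vs 9.5% (66 points rather than 73), and q = 20% gives 77.4% vs 19.0% (58 points). Power stays above 99%, so only the estimates move.

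**Step 7: type I error.** A simulation of 40,000 trials at 80 per arm and q = 10%, with both arms at 22%, gave 0.049 for the unadjusted, the restricted and the stratified (ISI ≥8 vs ≤7) analyses. Under 45% vs 22%, power was 0.761, 0.839 and 0.829 respectively.

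**The case against.** The strongest reply has four parts.

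First, a comparison of proportions between randomized arms has a natural default: everyone evaluable, with ISI ≤7 at follow-up as the outcome. On that reading the endpoint is computable and nothing is biased; the difference shrinks only relative to the ISI ≥8 subgroup. This is a fair point about the estimand. But the hypothesis is about people who stop meeting criteria, and the plan's own remark says everyone starts above the cut-off. Both point to the ISI ≥8 set, so the text supports two denominators and chooses neither.

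Second, the inputs to the power illustration are undocumented, and other values are kinder. With 50% vs 20%, power at 80 per arm is 98% at q = 0 and still 94% at q = 10% with everyone counted. The plan sets no power target for this endpoint. This stands: the figures show direction and possible size, not an expected loss.

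Third, restriction drops randomized people, and a stratified analysis that keeps everyone has nearly the same power (0.829 vs 0.839). This also stands as a reason to report an all-randomized adjusted analysis alongside. Restricting on a pre-randomization score still preserves the randomized comparison.

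Fourth, Section 4.3 labels scores below 7 as no clinically significant insomnia, whereas Section 9.1 uses ≤7, so a score of exactly 7 is classified inconsistently. That is a separate discrepancy; it does not remove this one.

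**Conclusion.** The concern holds. The 100% statement is not guaranteed on the scale that defines remission, and the treatment of people entering at ISI ≤7 is unstated. This follows from the text and needs no assumption.

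Its size is unknown. It depends on q, on the remission rates and on similar staying rates in the two arms, none of which the documents give. It is trivial at q = 2%. Under the assumed 45% vs 22%, it takes per-sex power at 10 weeks from 88% to 77% at q = 10%, of which restriction recovers part (84%). The per-sex figures are the relevant ones because Section 9.1 plans all analyses separately by sex; pooled power is barely touched up to q = 10%.

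Type I error is unaffected, the issue is confined to this secondary endpoint, and no effect on the primary ISI-change analysis is shown. It should be fixed before analysis because the same data can otherwise give two answers.

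**What to change.** In Section 9.1:

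- Delete or correct the 100% statement.
- Define the Hypothesis 1.2.1 analysis set as randomized participants whose pre-randomization (eligibility screening) ISI was ≥8, with remission as ISI ≤7 at 10 weeks and at 6 months.
- Report by arm the number entering at ISI ≤7.
- Add, as a supportive analysis, an all-randomized logistic model adjusted for pre-randomization ISI.

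Reconcile the cut-off wording in Section 4.3 with Section 9.1 at the same time. Scoring follow-up on the full three-part entry rule would also remove the mismatch, but it would replace the stated ISI ≤7 endpoint; restriction keeps it.

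The cost is wording, provided the screening ISI total is kept for everyone, including those who qualify on another route. The plan should say so. Section 3.5 states "Once consented and eligibility is confirmed, participants will be randomized using a permuted-block method", and Section 5.1 places screening in DatStat, while Section 4.2.1 places post-enrollment questionnaires in RICE. No section says whether the baseline ISI is the screening score. The statistical cost is a smaller denominator (0.9 × 80 = 72 per arm per sex at q = 10%) and a result that applies to survivors with ISI ≥8 at entry.

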#### **4.3. Study Procedures:**

##### **Assessment of Sleep**

1) Insomnia Severity Index (ISI) is a 7-item, Likert scale, self-report questionnaire assessing perception of sleep and consequences of insomnia. The ISI has had extensive validity and reliability testing, including for electronic delivery and for use in evaluating treatment response. Cronbach  $\alpha$  for internal consistency is 0.90, convergent validity with measures of fatigue, quality of life, anxiety and depression have been reported. The scores range from 0 (no insomnia) to 28 (severe insomnia); scores  $< 7$  are considered “no clinically significant insomnia”. The ISI will be administered at baseline, post-intervention, and 6-month follow-up.

2) Sleep Diary will be an online diary and will be included in the SHUTi program (including the patient education arm). Each diary entry contains 10 standard sleep questions including bedtime, sleep onset latency, number of awakenings, total length of awakenings, wake time, arising time, daytime naps, rating of soundness of previous night's sleep, rating of refreshed feeling upon morning awakening and inquiry about sleep aids (over the counter medication/alcohol). In addition to the 10 pre-assessment entries required before the intervention begins, participants are encouraged to complete the diary daily, but entries that are up to 3 days old will be accepted. Sleep diary data will generate data on sleep onset latency (SOL), wake after sleep onset (WASO), sleep efficiency (SE) and number of awakenings. Data from the sleep diaries will be correlated with actigraphy data.

3) Actigraphy will be collected to measure sleep-patterns of each participant. A WHOOP wrist monitor to be worn over 7 to 11 consecutive days at three specified intervals [baseline, post-intervention, 6 months]. Actigraphy provides objective assessment of wrist movement that infers wakefulness and sleep.

St. Jude Children's Research Hospital

IRB NUMBER: 19-0121

IRB APPROVAL DATE: 05/04/2021

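### The remission model for hypothesis 1.2.1 names no covariates; adding baseline ISI is a free improvement, worth some power if baseline ISI is prognostic

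*Combined protocol and SAP*

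**What the plan says.** Hypothesis 1.2.1 (section 1.2) is the remission hypothesis: "A larger proportion of survivors randomized to the CBTi intervention will no longer meet clinical criteria for insomnia post-intervention". Section 9.1, Statistical Analysis, sets remission at ISI of 7 or less and tests it at 10 weeks and 6 months, "noting that 100% of eligible participants will meet the criteria at randomization), using logistic regression models". No covariate is listed.

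Four other statements bear on the model:

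- **Primary analysis (section 9.1).** Mean ISI change is "compared between study arms using linear regression (adjusted for stratification factors". Baseline ISI enters by subtraction only, not as a covariate.
- **Randomisation (section 3.5).** Allocation uses a "permuted-block method with random block sizes, stratified on sex, age" (below 40 against 40 and over) and cranial radiation (yes/no).
- **Analysis by sex (section 9.1).** A priori, "we plan to carry out all analyses and report results separately by sex". A combined analysis is considered only if the effects look comparable.
- **Adjustment (section 9.1).** "Balance of patient characteristics between study arms will be evaluated and if necessary, adjusted comparisons will be carried out". Separately, cumulative doses of certain chemotherapies and of cranial radiation are to be covariates in analyses that the text calls relevant but does not list.

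On data, section 4.3 says: "The ISI will be administered at baseline, post-intervention, and 6-month follow-up".

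**The concern.** Reaching an ISI of 7 depends on where a participant starts. Someone at 9 needs a fall of 9 − 7 = 2 points; someone at 22 needs 22 − 7 = 15. The primary change score takes some account of this. The remission indicator takes none unless baseline ISI is put in the model.

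Two things are at stake. The first is power on a named hypothesis: the analyses are planned within sex, at about 80 per arm, and no power is stated for remission. The second is pre-specification: if adjustment waits on an observed imbalance, the covariate set stays open until the data have been seen.

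The sentence that defines the analysis also rests on a premise that the entry criteria do not secure. Section 3.1.3 admits a participant on delayed sleep onset or wake after sleep onset alone. Such a person may have an ISI of 7 or less at entry and so already satisfy the remission definition.

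**Working it through.** **1. The plan's own figures.** The plan gives minimum detectable effect sizes for the continuous ISI only (section 9.1, Power and sample size). With two-sided α = 0.05 and 80% power, the detectable effect is (1.960 + 0.842) × √(2/n per arm):

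- n = 80: 2.802 × 0.1581 = 0.443 (stated 0.45)
- n = 70: 2.802 × 0.1690 = 0.474 (stated 0.48)
- n = 160: 2.802 × 0.1118 = 0.313 (stated 0.31)

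All three reproduce. There is no remission figure to reproduce.

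**2. Inputs for remission.** From the documents: 80 per arm (one sex) and 160 per arm (combined), two-sided 0.05, and the three strata. Everything else is assumed:

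- control and CBTi remission of 20% v 40% or 30% v 52% at 80 per arm, and 20% v 34% or 30% v 45.5% at 160 per arm, chosen to put the arm-only model near 80% power;
- a correlation ρ between baseline ISI and a latent normal follow-up score, from 0 to 0.6;
- stratum effects of 0.2 SD each, with 0.4 SD as a strong case.

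**3. Check of the arm-only model.** Power = Φ{[|p₁ − p₀| − 1.96√(2p̄(1 − p̄)/n)] / √([p₀(1 − p₀) + p₁(1 − p₁)]/n)}. For 20% v 40% at 80 per arm: (0.20 − 1.96 × 0.0725)/0.0707 = 0.82, so power is 79.4%. The simulated arm-only values in this setting are 78.6% to 80.1%, which agrees.

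**4. Simulated power.** Wald tests, 2,000 replicates per cell. Each cell shows the arm-only model, then arm + strata + baseline ISI, in per cent, with the gain in points. Sex is among the strata only at 160 per arm.

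| Setting | ρ = 0 | ρ = 0.3 | ρ = 0.5 | ρ = 0.6 |
|---|---|---|---|---|
| 80/arm, 20% v 40% | 80.1 → 80.0 (−0.1) | 78.7 → 81.0 (+2.3) | 78.6 → 84.4 (+5.8) | 79.1 → 87.5 (+8.4) |
| 80/arm, 30% v 52% | 80.2 → 81.7 (+1.5) | 80.5 → 82.4 (+1.9) | 81.1 → 87.0 (+5.9) | 81.6 → 89.9 (+8.3) |
| 160/arm, 20% v 34% | 80.3 → 80.9 (+0.6) | 80.5 → 82.1 (+1.6) | 79.3 → 86.5 (+7.2) | 81.1 → 90.2 (+9.1) |
| 160/arm, 30% v 45.5% | 82.8 → 83.6 (+0.8) | 81.9 → 84.6 (+2.7) | 82.2 → 88.6 (+6.4) | 81.0 → 90.5 (+9.5) |

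**5. What the strata contribute.** Arm + strata against arm alone changes power by −0.1 to +1.6 points across these cells. In the strong case it gains 2.3 points at 160 per arm (79.9% to 82.2%) and 2.0 points at 80 per arm (78.8% to 80.8%). At ρ = 0, adding baseline ISI to the strata model changes power by −0.1 to +0.2 points, so there is no material penalty if it proves uninformative.

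**6. Type I error.** With no effect (4,000 replicates, 30% remission in both arms, ρ = 0.5), the three models reject in 4.9%, 5.3% and 5.2% of trials at 160 per arm, and in 4.7%, 4.6% and 4.9% at 80 per arm.

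**7. Limits.** Monte Carlo error on a single power value is about √(0.8 × 0.2/2000) = 0.9 points. Allocation was 1:1 overall and not blocked within strata. The 6-month sample of about 70 per arm per sex was not simulated, nor were entrants with ISI of 7 or less at baseline.

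**The case against.** The strongest reply is that silence is not exclusion. Section 9.1 nowhere says that the logistic model is unadjusted. A reader might infer that the plan commits to an unadjusted model, ignores all three strata and therefore loses power. The documents do not support that reading:

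- Sex is conditioned on by the sex-specific analyses. It is constant within each of them and could not be a covariate there.
- Cranial radiation may enter as a dose covariate, although the analyses concerned are not listed.
- Chance imbalance is addressed, loosely, by the balance check. Age group has no cover beyond that.
- The strata are worth only about 0 to 2 points of power.
- Any larger loss depends on a correlation and on remission rates that the documents do not give.

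It is also fair to say that remission is a secondary endpoint with no power claim, and that every model holds its type I error.

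All of that stands, and it limits the point to pre-specification plus a conditional gain. It does not remove it. The balance provision leaves both the variables and the trigger open. The statement about using the same analytic framework is attached to the continuous neurocognitive endpoints, so it does not carry the primary model's adjustment over to remission. None of these provisions names baseline ISI.

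**Conclusion.** The point holds as a minor one, a free improvement. The covariates of the remission model are not specified, and baseline ISI, already collected, is a named covariate in no model. If baseline ISI is prognostic, naming it with the strata gains about 1 to 3 points of power at a correlation of 0.3, about 6 to 7 at 0.5 and about 8 to 9.5 at 0.6. At a correlation of 0 baseline ISI adds essentially nothing. These sizes rest wholly on the assumed remission rates, correlations and stratum effects; only the sample sizes and α come from the plan. Power cannot be said to be lost as a settled fact, and the strata are chiefly a matter of consistency with the primary model.

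The claim that every entrant meets the criterion at randomisation does not follow from section 3.1.3, and the two places must be reconciled whatever model is chosen.

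**What to change.** Add to section 9.1, before outcome data are examined, that the logistic models for ISI of 7 or less at 10 weeks and at 6 months include arm, baseline ISI as a continuous covariate, age group and cranial radiation (yes/no), with sex added only when the sexes are combined. This should not depend on the balance check.

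Because adjustment makes the odds ratio conditional on the covariates, report a standardised (marginal) risk difference with its confidence interval beside it, and say which measure is the target.

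Separately, reconcile the 100% statement with section 3.1.3 and say how a participant who enters with ISI of 7 or less is counted. Adjusting for baseline ISI does not by itself define what no longer meeting the criterion means for such a person.

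The cost is a few sentences. All the covariates are already held, and no visit, measurement or participant is added.
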